7.2.1.3. ARIA-H (Superficial Siderosis)

Table 10: Disposition of ARIA-H (Superficial Siderosis) Cases

Clinical Symptom Severity	New Incident Areas of Superficial Siderosis ¹ (Central Read)		
	1	2	>2
Asymptomatic	Continue dosing at current dose and schedule	Suspend dosing. Once ARIA-H is stable the subject may resume dosing at the same dose.	Discontinue dosing
Mild	Suspend dosing. Once ARIA-H stabilizes and clinical symptoms resolve, the subject may resume dosing at the same dose.		
Moderate			
Severe			
Serious "other medically important event" ² only ³			
Serious, except for "other medically important event" ³	Discontinue dosing		

¹ New incident superficial siderosis = new incident superficial siderosis on treatment.

² "Other medically important events" requiring dose suspension include SAEs that are not life-threatening (in the opinion of the Investigator), do not require inpatient hospitalization or prolongation of existing hospitalization, and do not result in significant/permanent disability or congenital anomalies/fetal defects, but may (in the opinion of the Investigator) jeopardize the subject or may require intervention to prevent one of the outcomes listed above as described in Section 15.3.3.

³ SAEs requiring permanent discontinuation of study treatment include those that are life-threatening (in the opinion of the Investigator), require inpatient hospitalization or prolongation of existing hospitalization, and/or result in persistent or significant disability/incapacity or a congenital anomaly/birth defect as described in Section 15.3.3.

Asymptomatic ARIA-H (Superficial Siderosis)

- Subjects who develop a **single incident focal area of hemosiderosis (also referred to as superficial siderosis)** may continue treatment at the current dose, but must have an unscheduled visit for an MRI and MOCA as well as biomarker and PK sample collection every 2 weeks (± 3 days) until the superficial siderosis is confirmed as stable per the centrally read MRI. Superficial siderosis is considered stable if it is unchanged between 2 consecutive MRIs, including the initial detection MRI and the MRI performed 2 weeks (± 3 days) later.
- Subjects who develop **2 focal areas of hemosiderosis (superficial siderosis)** occurring at any time during the study will temporarily suspend treatment, but should complete all scheduled clinic visits for assessments and, in addition, have an unscheduled visit for an MRI and MOCA as well as biomarker and PK sample collection every 2 weeks (± 3 days) until the ARIA-H (superficial siderosis) is confirmed as stable per the centrally read MRI. Superficial siderosis is considered

CONFIDENTIAL

The information contained herein may not be used, disclosed, or published without the written consent of Biogen MA Inc.

stable if it is unchanged between 2 consecutive MRIs including the initial detection MRI and the MRI performed 2 weeks (± 3 days) later. Once the superficial siderosis is deemed stable, the subjects may resume treatment at the same dose. Only subjects who have not missed more than 4 consecutive doses will be allowed to resume treatment.

- Subjects who develop **>2 focal areas of hemosiderosis (superficial siderosis)** occurring at any time during the study must permanently discontinue treatment and should complete all scheduled clinic visits for assessments and, in addition, have an unscheduled visit for an MRI and MOCA as well as biomarker and PK sample collection every 2 weeks (± 3 days) until the ARIA-H (superficial siderosis) is confirmed as stable per the centrally read MRI. Superficial siderosis is considered stable if it is unchanged between 2 consecutive MRIs including the initial detection MRI and the MRI performed 2 weeks (± 3 days) later.

Symptomatic ARIA-H (superficial siderosis)

- Subjects who develop **≤ 2 new focal areas of superficial siderosis and mild, moderate, severe, or serious (“other medically important event” only)** clinical symptoms will temporarily suspend treatment, but should complete all scheduled clinic visits for assessments and, in addition, have an unscheduled visit for an MRI and MOCA as well as biomarker and PK sample collection every 2 weeks (± 3 days) until the ARIA-H superficial siderosis is confirmed stable per the centrally read MRI. Superficial siderosis is considered stable if it is unchanged between 2 consecutive MRIs including the initial detection MRI and the MRI performed 2 weeks (± 3 days) later. Once the ARIA-H (superficial siderosis) is deemed stable and the clinical symptoms have resolved, the subjects may resume treatment at the same dose. Only subjects who have not missed more than 4 consecutive doses will be allowed to resume treatment.
- Subjects who experience **serious (except “other medically important event” [Section 15.3.3]) clinical symptoms associated with ARIA-H (superficial siderosis)** will permanently discontinue treatment, but should complete all scheduled clinic visits for assessments and, in addition, have an unscheduled visit for an MRI and MOCA as well as biomarker and PK sample collection every 2 weeks (± 3 days) until the superficial siderosis is confirmed stable per centrally read MRI.

CONFIDENTIAL

The information contained herein may not be used, disclosed, or published without the written consent of Biogen MA Inc.

- Subjects who develop **>2 new focal areas of superficial siderosis** regardless of clinical symptom severity will permanently discontinue treatment, but should complete all scheduled clinic visits for assessments and, in addition, have an unscheduled visit for an MRI and MOCA as well as biomarker and PK sample collection every 2 weeks (± 3 days) until the superficial siderosis is confirmed stable per centrally read MRI.

See Section 7.2.1.6 for details on resumption of dosing when suspension occurs during the titration period and Section 7.2.1.7 for guidelines on resuming dosing after a recurrence of ARIA.

7.2.1.4. ARIA-H (Macrohemorrhage)

- Subjects who develop any new incident macrohemorrhage, regardless of symptom severity during the study, will permanently discontinue treatment, but should complete all scheduled clinic visits for assessments and, in addition, have an unscheduled visit for MRI and MOCA as well as biomarker and PK sample collection every 2 weeks (± 3 days) until the macrohemorrhage is confirmed stable per centrally read MRI.

7.2.1.5. Disposition of Coincident ARIA-H and ARIA-E Cases

Subjects who develop ARIA-H coincident with ARIA-E at any time during the study will follow the most restrictive guidelines. Prior to resuming treatment, where applicable, ARIA-E must resolve, ARIA-H must be deemed stable, and the subject must be asymptomatic. For example, if a subject experiences asymptomatic ARIA-H (1-4 microhemorrhages) coincident with ARIA-E assessed as moderate on MRI and accompanied by mild clinical symptoms, the dose should be suspended per the ARIA-E guidelines summarized in Table 11.

7.2.1.6. Resumption of Study Treatment After Suspension due to ARIA

7.2.1.6.1. MRI Monitoring

When treatment resumes after a dose suspension due to ARIA, an MRI and MOCA will be performed as well as biomarker and PK sample collection 2 weeks (± 3 days) after the second administration of the restarted dose if they do not have a scheduled MRI occurring during this period. In addition, if treatment was suspended during the dose titration prior to the subject reaching the maximum assigned dose, an MRI and MOCA will be performed as well as biomarker and PK sample collected 2 weeks (± 3 days) after the second administration of each increase in dose. MRIs will otherwise be performed as indicated in the Schedules of Events (Section 4.2).

7.2.1.6.2. Dosing Upon Resumption of Study Treatment

Subjects who suspend treatment due to ARIA for the first time may resume treatment at the same dose if they meet the criteria as described in Sections 7.2.1.1 to 7.2.1.5. Subjects who suspend and then resume dosing after having already reached their assigned top dose level are to continue dosing at that dose level. However, if dosing is suspended during the dose titration period, the

CONFIDENTIAL

The information contained herein may not be used, disclosed, or published without the written consent of
Biogen MA Inc.

subject (1) must receive at least 2 doses at the restart dose before titrating up to the next dose level and (2) must complete at least the required number of doses at that dose level per their assigned dosing regimen, as outlined in Table 11.

Table 11: Resumption of Study Treatment Following Dose Suspension Due to ARIA During Titration

Assigned Dosing Regimen (Maximum Dose)	Dose Level at Which ARIA Occurred	Number of Doses Prior to ARIA	Number of Doses Needed Before Going to the Next Higher Dose
ApoE ε4 (+)			
Low Dose (3 mg/kg)	1 mg/kg	1	2
High Dose (6 mg/kg)	1 mg/kg	1	2
	1 mg/kg	2	2
	3 mg/kg	1	3
	3 mg/kg	2	2
	3 mg/kg	3	2
	3 mg/kg	4	2
ApoE ε4 (-)			
Low Dose (6 mg/kg)	1 mg/kg	1	2
	1 mg/kg	2	2
	3 mg/kg	1	3
	3 mg/kg	2	2
	3 mg/kg	3	2
	3 mg/kg	4	2
High Dose (10 mg/kg)	1 mg/kg	1	2
	1 mg/kg	2	2
	3 mg/kg	1	2
	3 mg/kg	2	2
	6 mg/kg	1	2
	6 mg/kg	2	2

7.2.1.7. Management After Recurrent ARIA (Dosing and MRI)

If the subject has a second occurrence of ARIA (i.e., a second occurrence of ARIA-E or of ARIA-H, or ARIA-E and ARIA-H) that requires dose suspension, after the ARIA-E resolves or stabilizes, the subject is to resume dosing at the next lower dose and is to receive 2 doses at that

CONFIDENTIAL

The information contained herein may not be used, disclosed, or published without the written consent of Biogen MA Inc.

dose level (i.e., the restart dose) before titrating up to the next higher dose. Once dosing has resumed, the guidelines outlined in Table 11 apply, unless the subject has reduced from 1 mg/kg to placebo. In this case, the subject will remain on placebo for the duration of the placebo-controlled portion of the study. If a subject resumes treatment after ARIA, an MRI and MOCA will be performed as well as biomarker and PK sample collection 2 weeks (± 3 days) after the second administration of the restarted dose, and 2 weeks (± 3 days) after the second administration of each increase in dose unless the subject has a scheduled MRI during this period. MRIs will otherwise be performed as indicated in the Schedules of Events (Section 4.2).

If the subject experiences a third episode of ARIA that requires dose suspension, the subject must discontinue study treatment. Subjects who discontinue treatment are to remain in the study and continue all protocol-required tests and assessments.

Subjects who develop ARIA during the placebo-controlled period but continue or resume treatment at an active dose are eligible to enter the LTE period and will receive the lowest dose that they have tolerated during the placebo-controlled period. A subject who is switched to placebo but remains in the study may be titrated to aducanumab 1 mg/kg during the LTE period.

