7.2.1.1. Disposition of ARIA-E Cases

Table 8: Disposition of ARIA-E Cases

Clinical Symptom Severity	ARIA-E Severity on MRI (Central Read)		
	Mild	Moderate	Severe
Asymptomatic	Continue dosing at current dose and schedule	Suspend dosing. Once ARIA-E resolves the subject may resume dosing at the same dose.	
Mild	Suspend dosing. Once ARIA-E and clinical symptoms resolve, the subject may resume dosing at the same dose.		
Moderate			
Severe			
Serious "other medically important event" only ¹			
Serious, except for "other medically important event" ²	Discontinue Dosing		

¹ "Other medically important events" requiring dose suspension include SAEs that are not life-threatening (in the opinion of the Investigator), do not require inpatient hospitalization or prolongation of existing hospitalization, and do not result in significant/permanent disability or congenital anomalies/fetal defects, but may (in the opinion of the Investigator) jeopardize the subject or may require intervention to prevent one of the outcomes listed above and as described in Section 15.3.3.

² SAEs requiring permanent discontinuation of study treatment include those that are life-threatening (in the opinion of the Investigator), require inpatient hospitalization or prolongation of existing hospitalization, and/or result in persistent or significant disability/incapacity or a congenital anomaly/birth defect as described in Section 15.3.3.

- Subjects who develop **mild ARIA-E, per central MRI reading, with no clinical symptoms** at any time during the study may continue in the study at their current dose. Subjects should complete all scheduled clinic visits for assessments and, in addition, have an unscheduled visit for an MRI and MOCA as well as biomarker and PK sample collection approximately every 4 weeks until the ARIA-E has resolved per the centrally read MRI. The Sponsor may require that the subjects discontinue dosing or continue dosing at a lower dose level based on review of safety and MRI data.

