- Subjects who develop **moderate or severe ARIA-E, per central MRI reading, with no clinical symptoms** at any time during the study will temporarily suspend treatment, but should complete all scheduled clinic visits for assessments and, in addition, have an unscheduled visit for an MRI and MOCA as well as biomarker and PK sample collection approximately every 4 weeks until the ARIA-E has resolved per the centrally read MRI. If the ARIA-E has resolved and the subjects remain asymptomatic, the subjects may resume treatment at the same dose. Only subjects who have not missed more than 4 consecutive doses will be allowed to resume treatment.

CONFIDENTIAL

The information contained herein may not be used, disclosed, or published without the written consent of Biogen MA Inc.

- Subjects who develop **mild, moderate, or severe ARIA-E, per central MRI reading, accompanied by mild, moderate, severe, or serious (“other medically important event” only) clinical symptoms** at any time during the study will temporarily suspend treatment, but should complete all scheduled clinic visits for assessments and, in addition, have an unscheduled visit for an MRI and MOCA as well as biomarker and PK sample collection approximately every 4 weeks until the ARIA-E has resolved per the centrally read MRI. If the ARIA-E has resolved and the clinical symptoms have resolved, the subject may resume treatment at the same dose. Only subjects who have not missed more than 4 consecutive doses will be allowed to resume treatment.
- Subjects who develop **mild, moderate, or severe ARIA-E, per central MRI reading, accompanied by serious (except “other medically important event”) clinical symptoms** at any time during the study will permanently discontinue treatment. Subjects should complete all scheduled clinic visits for assessments and, in addition, have an unscheduled visit for an MRI and MOCA as well as biomarker and PK sample collection approximately every 4 weeks until the ARIA-E has resolved per centrally read MRI.

See Section 7.2.1.6 for details on resumption of dosing when suspension occurs during the titration period and Section 7.2.1.7 for guidelines on resuming dosing after a recurrence of ARIA.

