7.2.1.2. ARIA-H (Microhemorrhage)

In this study, new incident microhemorrhages are defined as new incident microhemorrhages that occur on treatment and do not include microhemorrhages at baseline.

CONFIDENTIAL

The information contained herein may not be used, disclosed, or published without the written consent of Biogen MA Inc.

Table 9: Disposition of ARIA-H (Microhemorrhage) Cases

Clinical Symptom Severity	New Incident Microhemorrhages ¹ (Central Read)		
	≥1 and ≤4	≥5 and ≤9	≥10
Asymptomatic	Continue dosing at current dose and schedule	Suspend dosing. Once ARIA-H is stable, the subject may resume dosing at the same dose.	Discontinue dosing
Mild	Suspend dosing. Once ARIA-H stabilizes and clinical symptoms resolve, the subject may resume dosing at the same dose.		
Moderate			
Severe			
Serious "other medically important event" only ²			
Serious, except for "other medically important event" ³	Discontinue dosing		

¹ New incident microhemorrhages = new incident microhemorrhages on treatment; does not include microhemorrhages at baseline.

² "Other medically important events" requiring dose suspension include SAEs that are not life-threatening (in the opinion of the Investigator), do not require inpatient hospitalization or prolongation of existing hospitalization, and do not result in significant/permanent disability or congenital anomalies/fetal defects, but may (in the opinion of the Investigator) jeopardize the subject or may require intervention to prevent one of the outcomes listed above as described in Section 15.3.3.

³ SAEs requiring permanent discontinuation of study treatment include those that are life-threatening (in the opinion of the Investigator), require inpatient hospitalization or prolongation of existing hospitalization, and/or result in persistent or significant disability/incapacity or a congenital anomaly/birth defect as described in Section 15.3.3.

Asymptomatic ARIA-H (Microhemorrhage)

- Subjects who develop a **≥1 and ≤4 new incident microhemorrhage(s)** at any time during the study may continue treatment at the current dose.

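### The restart rule after a second ARIA event lets dosing resume once ARIA-E merely stabilizes, while every other restart rule in the same protocol versions requires it to resolve

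*Protocol*

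**What the plan says.** References are to version 3.0 unless stated.

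- **Recurrence rule, Section 7.2.1.7.** It covers a second occurrence of ARIA-E, ARIA-H or both that requires dose suspension, and says that "after the ARIA-E resolves or stabilizes, the subject is to resume dosing at the next lower dose". Version 2.0 has the same sentence in Section 7.2.2.6.
- **Table 8 (ARIA-E disposition).** For symptomatic cases short of the discontinuation criterion: "Once ARIA-E and clinical symptoms resolve, the subject may resume dosing at the same dose". The cell for asymptomatic moderate or severe ARIA-E also requires resolution.
- **Section 7.2.1.1, text.** "If the ARIA-E has resolved and the clinical symptoms have resolved, the subject may resume treatment at the same dose". The asymptomatic bullet again requires resolution.
- **Section 7.2.1.5 (coincident ARIA-H and ARIA-E).** "Prior to resuming treatment, where applicable, ARIA-E must resolve, ARIA-H must be deemed stable, and the subject must be asymptomatic".
- **Table 9 (microhemorrhage).** Here stabilizing is said of ARIA-H: "Once ARIA-H stabilizes and clinical symptoms resolve, the subject may resume dosing at the same dose".

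**The concern.** The recurrence rule sets a weaker imaging condition for ARIA-E than the rest of the section, and it does so for subjects having their second event. Only episodes that require suspension come under it. For ARIA-E, under Table 8, these are episodes with symptoms or with moderate or severe findings on MRI. Followed literally, the sentence puts such a subject back on drug while the edema is unchanged but still present.

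Two other features of the sentence add to this. It directs resumption where Table 8 and Section 7.2.1.1 only permit it. It also does not repeat the conditions that symptoms have resolved and that no more than 4 consecutive doses have been missed. ARIA is the event of special interest in this program, so its restart rule should have a single reading.

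**Working it through.** No power, alpha or sample-size figure is involved. The check is a comparison of texts.

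**1. Count the statements on restarting after ARIA-E.**

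| Version | Requires resolution | Allows stabilization | Share requiring resolution |
|---|---|---|---|
| 3.0 | Table 8, two cells; 7.2.1.1, two bullets; 7.2.1.5, one statement = 5 | 7.2.1.7, one statement | 5 of 6 |
| 2.0 | Table 8, two cells; 7.2.1.1, two bullets; 7.2.2.4, one statement = 5 | 7.2.2.6, one statement | 5 of 6 |
| 1.0 | Table 6, three cells; 7.2.1.1, two bullets; 7.2.1.3, one statement = 6 | none | 6 of 6 |

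The count covers explicit conditions. It leaves out Section 7.2.1.6.2 (7.2.2.5.2 in version 2.0), which only refers back to the criteria in the other sections.

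**2. Is stable ARIA-E defined?** No. Sections 7.2.1.2 and 7.2.1.3 define stability for microhemorrhage and superficial siderosis as no change between two consecutive MRIs. Nothing equivalent exists for ARIA-E. The recurrence sentence also covers a second ARIA-H, yet gives no restart condition that names ARIA-H. Both facts suggest that the intended condition was ARIA-E resolved or ARIA-H stabilized.

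**3. Could the lower dose have been meant to replace resolution?** Version 1.0 argues against it. There the restart after suspension for ARIA was already at the next lower dose, and ARIA-E still had to have resolved first. Neither later version says that the requirement is relaxed at recurrence.

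**4. Do the other sections override the sentence?** Not clearly. The conditions in 7.2.1.1 and 7.2.1.5 apply to events whenever they occur in the study, so they can be read as still in force. However:
- Section 7.2.1.6.2 invokes the criteria of 7.2.1.1 to 7.2.1.5 expressly for a first suspension.
- Section 7.2.1.1 sends the reader to "Section 7.2.1.7 for guidelines on resuming dosing after a recurrence of ARIA".
- Section 7.2.1.7 then points only to Table 11 and the schedules in Section 4.2, and not back to the resolution criteria.

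A site following the cross-references therefore ends at the defective sentence. A second episode with ARIA-E and ARIA-H together falls under 7.2.1.5 and 7.2.1.7 at once, and the two give different answers.

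**5. Who would be re-exposed?** The dose levels are 1, 3, 6 and 10 mg/kg (Section 5.3). Under the literal reading, subjects on 3, 6 or 10 mg/kg at the second event restart at 1, 3 or 6 mg/kg. That is 1/3 = 33%, 3/6 = 50% or 6/10 = 60% of the previous dose. A subject on 1 mg/kg goes to placebo and is not re-exposed. These ratios describe the exposure; they do not measure harm.

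**The case against.** The case for leaving this alone has four parts.

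- **Superseded text.** The sentence stands in versions 2.0 and 3.0. A later version exists: its Section 16.2.2.2 refers to subjects enrolled under versions 1 to 3, and it raises the carriers' high dose to 10 mg/kg, so Table 11 at least would have needed revision. Its Section 7 is not available. This stands as a limit, because nobody can tell from these pages whether the wording survived. It does not remove the conflict, which lies within each of the two versions.
- **Evident meaning.** The rule covers both ARIA types, and the protocol pairs resolving with ARIA-E and stabilizing with ARIA-H. The harmless reading can be applied in practice; the hazardous one has no criterion behind it. That is probably the intent, but the sentence names ARIA-E alone.
- **Dependence on the other sections.** Whether an event requires suspension can be settled only from Tables 8 to 10 and the sections around them, so 7.2.1.7 cannot be used in isolation. True, but those sections are needed to decide on suspension. Their restart criteria are tied explicitly only to a first suspension.
- **Safeguards.** The sponsor and the principal investigator review every ARIA case (Section 7.2.1). MRI is repeated about every 4 weeks "until the ARIA-E has resolved per the centrally read MRI". The restart dose is lower, and an MRI follows the second restarted dose. These reduce the risk materially and hold the grade at minor.

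**Conclusion.** The concern holds, as a minor inconsistency in an operative safety rule. In versions 2.0 and 3.0 the recurrence sentence contradicts the five other restart statements for ARIA-E, and it uses a criterion that is undefined for ARIA-E. It is most likely a drafting slip, but the cross-references lead a site to it and do not correct it.

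The practical size cannot be given, because the protocol does not state how often a second ARIA-E is unchanged but unresolved. No sample size, power, error rate or analysis changes. The conclusion applies to versions 2.0 and 3.0; for the later version it depends on whether the sentence was kept.

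**What to change.** First check whether the later version still contains the sentence. If it does, replace the restart condition in the recurrence section with wording to this effect: after ARIA-E has resolved and/or ARIA-H is stable, as applicable, and the resumption criteria of Sections 7.2.1.1 to 7.2.1.5 are met, the subject may resume dosing at the next lower dose. Referring back to those sections restores the symptom and missed-dose conditions. Permitting resumption, rather than directing it, matches Table 8.

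The cost is one sentence, with no new procedures, visits or data.

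An optional correction can go in at the same time. Section 7.2.1.5 says that "the dose should be suspended per the ARIA-E guidelines summarized in Table 11", but Table 11 is the re-titration table; the ARIA-E guidelines are in Table 8.

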5.3.3. Long-Term Extension Period

Subjects who received aducanumab in the placebo-controlled period and who enter the LTE period will continue to receive the same dose of aducanumab that they were on at the end of the placebo-controlled period. Subjects who receive placebo during the placebo-controlled period and who enter the LTE period will be assigned to 1 of 2 treatment groups, based upon their ApoE ϵ 4 carrier status, in a 1:1 ratio (aducanumab low dose: aducanumab high dose). Subjects will be dosed using the same regimen described for the placebo-controlled period (see [Table 7](#) and [Figure 1](#)).

Any modifications to the dosing scheme (i.e. termination of high dose groups and replacement of titration with fixed dosing, as described in [Section 5.3.2](#)) will also be implemented in the LTE period.

CONFIDENTIAL

The information contained herein may not be used, disclosed, or published without the written consent of Biogen MA Inc.

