The total duration of study participation for each subject participating in the placebo-controlled period and the LTE period will be up to approximately 206 weeks, including a series of Screening visits within 8 weeks before administration of the first dose, a 76-week placebo-controlled treatment period, a 4-week FU period, a 100-week aducanumab dose-blind treatment period, and a safety FU period of approximately 18 weeks after the final dose. The FU period of 18 weeks is based on an estimated mean elimination half-life in humans of 16 to 24 days (mean approximately 20 days, based on results from the single ascending dose study [Study 221AD101]) and anticipated brain concentrations of aducanumab of less than one-third the EC₅₀ (inhibitory concentration at 50% of the maximum observed biologic effect) for binding fibrillar amyloid at 8 weeks after the last dose.

During the placebo-controlled period, ApoE ϵ 4 carriers will receive placebo, aducanumab 3 mg/kg, or aducanumab 6 mg/kg whereas ApoE ϵ 4 non-carriers will receive placebo, aducanumab 6 mg/kg, or aducanumab 10 mg/kg. Aducanumab will be titrated for up to 6 doses prior to reaching the target dose as shown in [Table 7](#) and [Figure 1](#). Subjects who received

CONFIDENTIAL

The information contained herein may not be used, disclosed, or published without the written consent of Biogen MA Inc.

aducanumab in the placebo-controlled period and who enter the LTE period will receive the same dose of aducanumab that they received at the end of the placebo-controlled period (up to 6 mg/kg and 10 mg/kg in ApoE ϵ 4 carriers and non-carriers, respectively). Subjects who received placebo during the placebo-controlled period and who enter the LTE period will be assigned to treatment based upon their ApoE ϵ 4 carrier status in a 1:1 ratio (aducanumab low dose: aducanumab high dose); aducanumab will be titrated for up to 6 doses prior to reaching the target dose following the same schedule described for the placebo-controlled period.

See Section 5.3.2 for details of dosing scheme modification.

Individual dose adjustments may also be implemented to subjects who develop ARIA. See Section 7.2.1.

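### Protocol version 3.0 gives two incompatible extension-entry doses for aducanumab subjects with prior ARIA

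*Protocol*

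**What the plan says.** All references are to protocol version 3.0 unless stated.

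- **Section 5.3.3** (LTE dosing): subjects who received aducanumab "will continue to receive the same dose of aducanumab that they were on at the end of the placebo-controlled period". It makes no exception for ARIA. It does name the changes that carry over into the extension, namely termination of a high-dose group and replacement of titration by fixed dosing. ARIA is not among them.
- **Section 7.1** (overview) repeats the rule: subjects "who enter the LTE period will receive the same dose of aducanumab that they received at the end of the placebo-controlled period". Shortly afterwards it adds "Individual dose adjustments may also be implemented to subjects who develop ARIA" and refers to Section 7.2.1, without mentioning LTE entry.
- **Section 7.2.1.7** (headed as management of recurrent ARIA) sets a different entry dose for anyone with ARIA, first or recurrent, who was still on active drug or had gone back to it. Such a subject is described as "eligible to enter the LTE period and will receive the lowest dose that they have tolerated during the placebo-controlled period".
- **Section 7.2.1.6.2**: "Subjects who suspend treatment due to ARIA for the first time may resume treatment at the same dose". In addition, "Subjects who suspend and then resume dosing after having already reached their assigned top dose level are to continue dosing at that dose level".

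Versions 1.0 and 2.0 contain the same pair of rules. In version 1.0 the tolerated-dose sentence follows a table under which suspended subjects resumed one dose level lower (Section 7.2.1.4). Version 2.0 changed first resumption to the same dose (Section 7.2.2.5.2) and kept the sentence (Section 7.2.2.6). Version 3.0 kept it again.

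**The concern.** Both rules say what a subject will receive, and both cover the aducanumab subject who had ARIA and is still on active drug at Week 78. A site or dosing system that follows Section 5.3.3 and one that follows Section 7.2.1.7 could dose subjects with the same history differently for 26 infusions. The extension is dose-blind, so investigators are poorly placed to notice.

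The statistical stake is the extension summary. Section 16.2.2.6.2 presents LTE analyses by treatment group of the placebo-controlled period. Section 5.3 describes ARIA incidence as dependent on dose and on ApoE ε4 carriage. A mixture of doses under one group label would therefore be selected by a safety event and concentrated in the groups with more ARIA.

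**Working it through.** The plan states no figure on this point, and sample size, power and alpha are not involved. The check sets the rules side by side and reads the doses from Table 7.

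**Step 1: can the two rules differ?** Call the rule in Sections 5.3.3 and 7.1 rule A (end-of-period dose) and the rule in Section 7.2.1.7 rule B (lowest tolerated dose). They would coincide if ARIA always led to a lasting reduction. In version 3.0 it does not:

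- Dosing continues unchanged with asymptomatic mild ARIA-E (Table 8), 1 to 4 new microhemorrhages (Table 9) or one area of superficial siderosis (Table 10).
- After a first suspension, dosing resumes at the same dose (Section 7.2.1.6.2).
- After a second suspension, dosing resumes one level lower and is titrated up again after two doses (Section 7.2.1.7).

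A subject in any of these situations can therefore be at the assigned top dose at the end of the period.

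**Step 2: what does each rule give?** Table 7 shows every active regimen with two doses at 1 mg/kg. E is the end dose if the assigned level is reached. L is the lowest dose received, assumed tolerated, which is the most literal reading of rule B. The last column holds the entry dose constant over the 26 LTE doses.

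| Regimen (version 3.0) | E, rule A | L, rule B literal | E/L | 26 × E against 26 × L (mg/kg) |
|---|---|---|---|---|
| Carrier, low | 3 | 1 | 3 | 78 against 26 |
| Carrier, high | 6 | 1 | 6 | 156 against 26 |
| Non-carrier, low | 6 | 1 | 6 | 156 against 26 |
| Non-carrier, high | 10 | 1 | 10 | 260 against 26 |

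**Step 3: does the conflict need the literal reading?** Suppose rule B means the lowest dose reached through a reduction for ARIA. A first ARIA at top dose then produces no difference. A second suspension at top dose still does. A high-dose non-carrier goes from 10 to 6 and back to 10, so rule A gives 10 and rule B gives 6 (10/6 = 1.7-fold). A high-dose carrier goes from 6 to 3 and back to 6, so rule A gives 6 and rule B gives 3 (2-fold). The conflict survives, but in fewer subjects and with a smaller gap.

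**Step 4: effect on a group mean.** The documents give no share s of LTE entrants with prior ARIA. With s assumed between 5% and 40%, the literal reading of rule B, and E for everyone else, mean entry dose = (1 − s) × E + s × L:

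- Non-carrier, high: 0.95 × 10 + 0.05 × 1 = 9.55, down to 0.60 × 10 + 0.40 × 1 = 6.4, instead of 10 mg/kg.
- Carrier, high (and non-carrier, low): 0.95 × 6 + 0.05 × 1 = 5.75, down to 0.60 × 6 + 0.40 × 1 = 4.0, instead of 6 mg/kg.
- Carrier, low: 0.95 × 3 + 0.05 × 1 = 2.9, down to 0.60 × 3 + 0.40 × 1 = 2.2, instead of 3 mg/kg.

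These are upper limits on the dilution for each s. They put every ARIA subject at 1 mg/kg, and they compare with the full assigned dose, although some ARIA subjects would be below it at Week 78 under rule A as well.

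**The case against.** The strongest reply is that this is a general rule with a specific exception. Section 7.1 points to Section 7.2.1 for ARIA adjustments, and Section 7.2.1.7 lies within it. That is a fair reading of Section 7.1. It does not settle the matter: the pointer does not mention LTE entry, Section 5.3.3 has no pointer, and even if the exception governs, the text does not say which dose counts as the lowest tolerated.

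It can also be said that 1 mg/kg is an unlikely meaning. The next sentence of Section 7.2.1.7 treats 1 mg/kg as the special case for a subject who was switched to placebo, and in version 1.0 the sentence followed a step-down table. This has force. It is why the 6-fold and 10-fold figures are the most literal case and not an expected size.

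Two practical points limit the harm. The sponsor and the principal investigator review all ARIA cases for dosing decisions (Section 7.2.1), and dosing is recorded on the CRF (Section 15.4.2). Both reduce inconsistent application, but neither supplies the missing rule.

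Finally, version 3.0 is not the latest text. The statistical section of a later version (16.2.2.2) refers to subjects enrolled under versions 1 to 3 and lists 10 mg/kg as the high dose for carriers. Its Sections 5 and 7 are not shown. The point is therefore established for versions 1.0 to 3.0 only, and the carrier figures apply to version 3.0 doses.

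A reader might go further and infer that the extension cannot describe long-term treatment at the assigned regimen. The documents do not support that. The LTE objectives (Section 6.4.1) concern aducanumab treatment in general, Section 16.2.2.6.2 leaves the analysis details to the SAP, and subjects without ARIA fall under one rule only.

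**Conclusion.** The inconsistency is real in version 3.0. For aducanumab subjects with prior ARIA who are on active drug at Week 78, two sections give one entry dose and a third can give another, and the term used in the third does not define a single dose. The gap for an individual ranges from none, through 1.7- to 2-fold after a second ARIA at top dose on the narrower reading, to 6-fold (high-dose carrier) or 10-fold (high-dose non-carrier) on the most literal one. How many subjects are affected cannot be derived from the documents; the 5% to 40% range is an assumption.

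The consequence is limited. Subjects with the same history could be dosed differently, and extension results by original group would mix doses within the ARIA subset, mainly where ARIA is more frequent. The primary and secondary Week 78 endpoints are untouched. The conclusion rests on the version 3.0 text; its status in the later version is unknown.

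**What to change.** Reconcile Sections 5.3.3, 7.1 and 7.2.1.7 so that one extension-entry dose rule applies to subjects with prior ARIA. State it in one place, refer to it from the other two, and programme it in the IRT. If the concept of a tolerated dose is kept, define it so that each dosing history leads to exactly one dose. Make clear whether the rule covers any ARIA or only recurrent ARIA, since the heading and the wording of Section 7.2.1.7 differ on this. Which rule applies is for the sponsor to decide, and no view on that is given here.

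First check Sections 5 and 7 of the later version. If the conflict is already resolved there, only the handling of subjects who entered the extension under the older text needs documenting.

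The cost is about one paragraph in an amendment and an IRT check, with no added subjects, visits or procedures.
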